8.0 Data Collection and Management Procedures

Each subject is given a unique number and there is a password-protected master key database separate from the study to data link the subject to the code. This is only accessible to the PI. Coded data set with indirect identifiers and key stored separately and re-identified only when in use.

9.0 Data Analysis

Statistical Analysis: The initial analysis will be descriptive and will characterize the study groups in terms of study variables such as age, gender, education, and measures of overall medical burden etc. Categorical variables, nominal and ordinal, will be summarized by frequencies. Continuous variables will be summarized by the mean, standard deviation, 95% confidence intervals, median, and range. Where continuous variables cannot reasonably be considered to be

normally distributed, transformations (e.g. log, square root, or cube root transformation for skewed data) to achieve a normal distribution will be explored. Care must be taken to avoid placing too much emphasis on chance associations. As noted below, both unadjusted and false discovery rate p-levels will be reported basing the adjustment on the numbers of tests performed within each area. Specific Aims 1 and 2 will be analyzed using a repeated-measures analysis of variance (ANOVA) with FA, RD, and MWF as dependent variables. Specific Aim 3 will be analyzed using bivariate correlations and partial correlations (controlling for age) between changes in FA, RD, and MWF and changes in executive function and processing speed performance scores.

Sample Size/Statistical Design: There will be a total of 30 participants by the end of the study period. Data from this initial sample will be used for power calculations to determine the appropriate sample size for future studies.

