3.0 Objectives/Aims

The purpose of this proposed multidisciplinary, translational pilot study is to examine changes in white matter integrity using complementary neuroimaging techniques: high angular diffusion tensor imaging (HARDI) and multi-component relaxometry (MCR), in a population of participants clinically indicated to receive thyroid hormone for hypothyroidism. We will scan patients with hypothyroidism when they initiate treatment to determine baseline levels of white matter integrity and then rescan them three months and six months after starting thyroid hormone treatment to determine changes in white matter integrity. Given our sensitive and specific biomarkers of myelin integrity, we hypothesize that thyroid hormone treatment will be associated with an increase in white matter cohesion, i.e., fractional anisotropy as measured by HARDI, white matter microstructure as measured by HARDI (radial diffusivity), and MCR markers of improved myelination (myelin water fraction). In addition, we hypothesize that increases in white matter integrity will be correlated with improvements in cognition and mood. If successful, this will be

the first demonstration of improved white matter integrity with thyroid hormone replacement and pave the way for reparative therapies designed to restore structural brain connectivity.

Specific Aim 1: To measure white matter integrity at the initiation of thyroid hormone replacement and after euthyroid status using HARDI

Hypothesis 1: Participants diagnosed with hypothyroidism that become euthyroid will show improved white matter integrity measured by increasing fractional anisotropy and decreasing radial diffusivity.

Specific Aim 2: To measure white matter integrity at the initiation of thyroid hormone replacement and after euthyroid status using multicomponent relaxometry

Hypothesis 2: Participants diagnosed with hypothyroidism that become euthyroid will show improved white matter integrity measured by increasing myelin water fraction

Specific Aim 3: To correlate changes in white matter integrity with improvement in cognition and mood

Hypothesis 3: Improvement in white matter integrity will be positively correlated with cognitive function indicated by faster psychomotor processing speeds and improved executive function and with mood measured with lower depression severity ratings

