All assessments will be completed at baseline (within one week of initiating treatment), 3 months follow-up and 6 months follow-up (Table 1). PHQ-9 will be administered biweekly in between behavioral/MRI sessions. It is important to note that since levothyroxine has a long half-life (6-7 days), measurements within one week are appropriate for baseline assessments. Additionally due to this long half-life, there are no acute effects of treatment that would be missed at baseline. Assessment time points at 3 months and 6 months were chosen based on preclinical and clinical studies. DTI measures normalized in the aforementioned animal studies 3 months after TH administration (4). In clinical settings, patients might require several dose adjustments to achieve the thyrotropin goal. The usual dose adjustment intervals used in clinical

practice are 6-8 weeks. In a study by Duyff et al. evaluating the neuromuscular findings in thyroid dysfunction, hypothyroid patients reached biochemical euthyroidism in an average of 19 weeks (range 7 - 41 weeks) (35). Most studies to show improvement in mood and/or cognition had a follow-up time of 6 months (24).

Baseline	3 months	6 months
TFTs	TFTs	TFTs
Behavioral assessment	Behavioral assessment	Behavioral assessment
MRI	MRI	MRI

Table 1. Timeline for clinical, behavioral and neuroimaging assessments

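### Section 9.0 tests FA, RD and MWF by repeated-measures ANOVA alone; adding change estimates with confidence intervals from all available scans, a missing-scan rule and a sphericity correction would be a cheap improvement

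*Combined protocol and SAP*

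**What the plan says.** Section 9.0 (Data Analysis) gives one inferential method for Aims 1 and 2: they "will be analyzed using a repeated-measures analysis of variance (ANOVA"), with FA, RD and MWF as dependent variables. It names no time levels, contrast, sphericity correction or rule for missing scans.

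The number of levels has to be inferred from Section 6.0: "All assessments will be completed at baseline (within one week of initiating treatment), 3 months follow-up and 6 months follow-up (Table 1"). Table 1 there lists MRI and thyroid function tests at all three visits.

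Hypothesis 1 in Section 3.0 is directional and conditional: "Participants diagnosed with hypothyroidism that become euthyroid will show improved white matter integrity measured by increasing fractional anisotropy and decreasing radial diffusivity". Hypothesis 2 has the same form for MWF.

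Section 9.0 also contains two things that help. It promises descriptive summaries ("Continuous variables will be summarized by the mean, standard deviation, 95% confidence intervals, median, and range"), and Aim 3 uses "bivariate correlations and partial correlations (controlling for age) between changes in FA, RD, and MWF" and the cognitive scores. On size and purpose it says "There will be a total of 30 participants by the end of the study period" and "Data from this initial sample will be used for power calculations to determine the appropriate sample size for future studies".

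**The concern.** A future power calculation needs the mean change, its SD and its precision. The default visit test in a three-level ANOVA supplies none of these directly. It asks whether the three visit means differ in any direction, in everyone, whereas the hypotheses ask whether a measure moves one way in those who become euthyroid. The thyroid tests taken at each visit are not used in the analysis of Aims 1 and 2.

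In its classical form the ANOVA also keeps only participants with all three scans. Someone scanned at baseline and 6 months but not at 3 months contributes nothing, although their 6-month change was observed. With 30 participants, losing such pairs widens the estimate that the pilot exists to provide.

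Finally, with three levels the F test relies on sphericity. If that fails and no correction is applied, the type I error rises above its nominal level.

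**Working it through.** **Inputs.** From the documents: 30 participants in one group (Section 9.0) and three scan visits (Section 6.0). The documents give no alpha, effect size, within-person correlation or missing rate, and 30 comes with no calculation, so there is no power figure to reproduce. Assumed here: standardised change dz = mean change / SD of change = 0.5 at 6 months (range 0.3 to 0.7), two-sided 5% per measure, baseline always scanned, and each follow-up scan missing independently with probability m = 10% or 20%.

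**Usable participants.**
- Three-scan completers: 30(1 − m)² = 24.3 at 10% and 19.2 at 20%.
- Baseline/6-month pairs: 30(1 − m) = 27.0 and 24.0.
- Difference (only the 3-month scan missing): 30 × 0.9 × 0.1 = 2.7 and 30 × 0.8 × 0.2 = 4.8.

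**Power for the 6-month change.** Paired t-test, n − 1 degrees of freedom, noncentrality dz√n, averaged over the binomial distribution of n. With no scans missing the noncentrality is 0.5√30 = 2.74 and power is 75.4%.

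| dz | m | Completers | All pairs | Gain (points) |
|---|---|---|---|---|
| 0.3 | 10% | 29.4% | 32.3% | 2.9 |
| 0.3 | 20% | 23.8% | 29.1% | 5.3 |
| 0.5 | 10% | 65.4% | 70.5% | 5.0 |
| 0.5 | 20% | 54.3% | 64.8% | 10.6 |
| 0.7 | 10% | 90.7% | 93.7% | 2.9 |
| 0.7 | 20% | 81.9% | 90.3% | 8.5 |

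(Gains are from unrounded values.)

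**Precision.** Simulated 95% CI half-widths in SDs of change, completers against pairs: 0.417 and 0.392 at 10% (0.392/0.417 = 0.94, 6% narrower); 0.477 and 0.420 at 20% (0.88, 12% narrower).

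**Other comparator.** If the 6-month contrast in completers uses the ANOVA's pooled error under compound symmetry, simulation puts the gain from pairs at about 2 to 4 points (10%) and 8 to 9 (20%).

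**Mixed model.** A REML model with unstructured covariance on all scans, dz 0.5, correlation 0.8 (compound symmetry) or AR(0.8), gives 71.7–73.2% at 10% and 66.5–69.3% at 20%. That is about 1 to 4 points above all pairs. A separate calculation from generalised least squares information gives 1.1 to 4.5.

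**Pure dropout.** If everyone missing at 3 months is also missing at 6 months, completers and pairs are the same people and the gain from pairs is zero. With 10% lost by 3 months and 20% by 6, the mixed model adds 2 to 4 points (63.8% to 65.4% under compound symmetry; 65.8% to 69.3% under AR).

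**Against the omnibus test.** Uncorrected completer ANOVA against the mixed-model 6-month contrast, dz 0.5:

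| Pattern | Complete scans | 10% missing | 20% missing |
|---|---|---|---|
| Compound symmetry, linear | 66.6% v 75.8% | 56.4% v 71.7% | 45.6% v 66.7% |
| Compound symmetry, plateau by 3 months | 78.6% v 74.8% | 69.1% v 72.1% | 56.1% v 66.5% |
| AR(0.8), linear | 77.0% v 75.9% | 67.0% v 72.8% | 56.0% v 68.7% |
| AR(0.8), plateau by 3 months | 89.9% v 74.9% | 81.5% v 73.2% | 70.7% v 69.3% |

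Neither test dominates. In the last row the contrast is 15 points worse with complete scans and 8 worse at 10% missing. With Greenhouse-Geisser the omnibus figure at 10% missing is about 79%, still ahead.

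**Sphericity.** ε = (λ₁ + λ₂)² / [2(λ₁² + λ₂²)], with λ the variances of the linear and quadratic contrasts.
- AR(0.8): λ = 0.36 and 0.147, so ε = 0.85. Simulated type I error is 5.6% uncorrected and 4.7% with Greenhouse-Geisser.
- Correlations 0.9/0.9/0.7: λ = 0.30 and 0.033, so ε = 0.61. Type I error is 7.3% uncorrected and 4.8% corrected.

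**Euthyroid share.** Section 6.0 cites a mean of 19 weeks to euthyroidism, range 7 to 41. Those figures alone allow at most (41 − 19)/(41 − 13) = 79% euthyroid by 13 weeks and guarantee only 1 − (19 − 7)/(26 − 7) = 37% by 26 weeks. The bounds are wide and come from one cited study. They show only that euthyroid status at a scan cannot be taken for granted.

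**The case against.** The strongest reply is that three levels are an inference. Aim 1 is worded as two occasions, "To measure white matter integrity at the initiation of thyroid hormone replacement and after euthyroid status using HARDI". If the ANOVA compares baseline with one post-euthyroid scan, it is a paired t-test: no sphericity issue, no 2-df test and no loss from a missing intermediate scan. Three scheduled scans make three levels the likelier reading, but Section 9.0 does not settle it. That stands, and is itself a reason to write the levels down. Likewise, the documents neither confirm nor exclude deletion of incomplete participants; it is a property of the classical method.

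A reader might infer that the plan forfeits 5 to 10 points of power. The documents do not support that. The comparison is between two analyses of the 6-month change, neither of which Section 9.0 names, and against the omnibus test the contrast may win or lose. Section 6.0's animal rationale, with diffusion measures normalised at 3 months, makes an early plateau a plausible pattern. The missing-scan cost also disappears if the 30 are all completers, which the sample-size sentence allows, or under pure dropout; Section 5.0 tells participants they may withdraw at any time.

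A reader might also infer that the mean change and its SD cannot be obtained. They can: the descriptive summaries and the Aim 3 change scores make them available. What is absent is a commitment to report them.

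Nor does the all-pairs analysis relax the missing-completely-at-random requirement. Only the mixed model, which needs missing at random, does that.

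**Conclusion.** The point holds as a cheap improvement, not a flaw that invalidates the plan. The gaps that need no missing-data assumption are the unstated time levels, the absent commitment to a change with its CI, and the lack of any analysis tied to euthyroid status, which the hypotheses name. The sphericity correction matters only if three levels are used, and is small at AR(0.8).

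The missing-scan part is worth about 5 points of power at 10% missing and about 10 at 20% for the 6-month change. It rests on dz 0.5, two-sided 5% and independent missingness, none of which is in the documents. It is smaller at dz 0.3 or 0.7 and against a pooled-error contrast. Because the omnibus test is sometimes the more powerful one, it should be kept alongside the change estimates rather than replaced by them.

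**What to change.** Extend the ANOVA sentence in Section 9.0 along these lines:

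> FA, RD and MWF will each be compared across baseline, 3 and 6 months by repeated-measures ANOVA with a Greenhouse-Geisser correction [or: by a REML linear mixed model on all available scans, with visit as a factor]. For each measure, the mean change from baseline to 3 months and to 6 months will be reported with its SD and 95% CI from every available pair, overall and, descriptively, in participants biochemically euthyroid at that scan, by a definition fixed before analysis and using that visit's thyroid function tests. The [3- or 6-month] change is the main estimate. Missing and excluded scans will be counted by visit.

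Section 6.0 gives grounds for either time point: the animal findings for 3 months, the cited 19-week mean for 6. What matters is that the choice precedes the analysis. The ANOVA option with all-pairs estimates gets most of the benefit; the mixed model adds a little power and the weaker missing-data assumption.

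The cost is wording only: no new data or visits, and standard software. The euthyroid estimate uses fewer people, selected after baseline, so it should stay descriptive. Any added p-values count towards the false discovery rate adjustment that Section 9.0 already plans.

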4.0 Eligibility

4.1 Inclusion Criteria

a) Age: 21-60 years of age; b) a diagnosis of primary hypothyroidism from autoimmune thyroiditis (Hashimoto); c) able to give informed consent.

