6.0 Study Design and Procedures

All participants will be treated for their hypothyroidism according to the standard of care as reflected in recent guidelines from the American Thyroid Association (27). As part of the initial screening, after informed consent is obtained, all participants will receive the following clinical tests/instruments: 1) The Cumulative Illness Rating Scale (CIRS-G;(28)); 2) The Cerebrovascular Risk Factor Scale (CVRF (29)); (stroke risk factor)

developed by the American Heart Association; 3) Patient Health Questionnaire (PHQ-9) (30)); 4) The Inventory of Depressive Symptomatology (IDS-C/IDS-SR;(31)); 5) the Montreal Cognitive Assessment (MoCA (32)); 6) Relevant laboratory studies such as complete and differential blood counts, serum chemistry, thyroid function tests; 7) A brief neuropsychological protocol focused on cognitive domains of executive function, attention, and psychomotor processing (33). *Thyroid Status Assessment:* All participants will have blood work done to obtain thyroid functions tests (TFTs): thyroid stimulating hormone (TSH), Free T4, T3, anti-thyroglobulin and anti-thyroid peroxidase (TPO) antibodies. All participants will receive *the same treatment* (levothyroxine, a synthetic T4 hormone replacement) at a dose that will be titrated using serum thyrotropin (TSH) levels as a goal, according to the American Thyroid Association Task Force recommendations (27). *Behavioral Assessment:* Depression severity will be assessed with the PHQ-9 and the IDS. Global cognitive function will be measured with the MoCA. Executive function, attention and processing speed will be assessed using the following tests from the NIH Toolbox: Dimensional Change Card Sort Test, Flanker Inhibitory Control and Attention Test and the Pattern Comparison Processing Speed Test (33). These tests have been shown to have good test-retest reliability and standardized effect sizes for practice effects (34). We will examine whether performance improvements at subsequent assessment time points exceed what would be expected due to practice effects.

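### Should the Aim 3 correlations also be adjusted for change in thyroid function, and not only for age?

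*Combined protocol and SAP*

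**What the plan says.** Section 3.0 sets Aim 3 as correlating change in white matter integrity with improvement in cognition and mood. Hypothesis 3 predicts a positive correlation. Neither claims that the correlation is independent of thyroid recovery, or that white matter mediates the cognitive gain.

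Section 9.0 gives the analysis as "bivariate correlations and partial correlations (controlling for age", applied to changes in FA, RD and MWF against changes in executive function and processing speed. Age is the only covariate. On multiplicity, "both unadjusted and false discovery rate p-levels will be reported basing the adjustment on the numbers of tests performed within each area". The section sets a total of 30 participants and says the data will inform sample-size planning for later studies.

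Section 6.0 shows that thyroid data will exist: "All participants will have blood work done to obtain thyroid functions tests (TFTs". Table 1 places these tests at baseline, 3 and 6 months, alongside MRI and behavioral assessment. Levothyroxine is "titrated using serum thyrotropin (TSH) levels as a goal". The cognitive tests are the "Dimensional Change Card Sort Test, Flanker Inhibitory Control and Attention Test and the Pattern Comparison Processing Speed Test". No analysis in Section 9.0 names a thyroid variable.

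**The concern.** The protocol's own rationale supplies a possible common cause. Thyroid hormone is the intended driver of white matter change (Sections 1.0 and 3.0), and Section 2.0 cites studies in which replacement improved executive function and attention. If people who recover more thyroid function gain more on both, the two changes will correlate even with no direct link between them.

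Recovery is likely to vary. Section 4.1 asks for "a diagnosis of primary hypothyroidism from autoimmune thyroiditis (Hashimoto" and sets no TSH limit. Section 6.0 cites a study in which "hypothyroid patients reached biochemical euthyroidism in an average of 19 weeks (range 7 - 41 weeks". False-discovery control guards against chance associations, not against a shared cause.

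At stake is how a positive Aim 3 result is read: as a sign that restored white matter carries cognitive benefit, or as two measures recovering in parallel. Later studies planned from these data might inherit the ambiguity. A partial correlation that also controls for change in log TSH looks like a cheap remedy, since the blood tests are already scheduled.

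**Working it through.** **Inputs.** n = 30 (Section 9.0). Two-sided alpha of 0.05 is assumed, as the protocol states none. The documents give no strength for the thyroid links, so every loading (correlation with thyroid change) and reliability below is an assumption. Section 9.0 derives no figure for Aim 3, so there is none to reproduce.

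**1. What shared recovery alone produces.** If the imaging and cognitive changes each load *a* on thyroid change and have no other link, their correlation is *a*². Simulation at n = 30, single test, adjusted for age:

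| Loading *a* | *a*² | Mean age-adjusted r | Significant |
|---|---|---|---|
| 0.3 | 0.09 | 0.09 | 7.5% |
| 0.5 | 0.25 | 0.25 | 27% |
| 0.6 | 0.36 | 0.36 | 50% |
| 0.7 | 0.49 | 0.48 | 79% |

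If either loading is zero, the rate is 5%. With nine tests (three imaging measures by three scores) under Benjamini-Hochberg adjustment, at least one passes in about 9%, 36%, 66% and 91% of trials at the same four loadings. In every row the true correlation is *a*², not zero, so Hypothesis 3 as worded is true and its detection is not a type I error.

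**2. The direct cost of a thyroid covariate.** Critical |r| = t / √(df + t²).
- Age only: df = 27, t = 2.052, giving 0.367.
- Age plus thyroid: df = 26, t = 2.056, giving 0.374.

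The loss of one degree of freedom is negligible.

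**3. What the adjusted estimate shows when there is no link.** With thyroid change measured at reliability ρ, the partial correlation left over is (*a*² − *a*²ρ) / (1 − *a*²ρ). At *a* = 0.7 and ρ = 0.8 this is (0.49 − 0.392) / (1 − 0.392) = 0.098 / 0.608 = 0.16 (simulated mean 0.159). Shared cause is reduced but not removed.

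**4. What it shows when there is a link.** Let thyroid act on cognition only through white matter, with observed r = 0.5, loading 0.7, imaging reliability 0.6 and TSH reliability 0.8.
- True white matter with score: 0.5 / √0.6 = 0.645.
- Observed imaging with TSH: 0.7 × √0.6 × √0.8 = 0.485.
- Score with TSH: 0.7 × 0.645 × √0.8 = 0.404.
- Partial r = (0.5 − 0.485 × 0.404) / √[(1 − 0.485²)(1 − 0.404²)] = 0.304 / 0.800 = 0.38 (simulated mean 0.375).

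Adjustment shrinks a real effect. Power falls from about 81% to 44% at imaging reliability 0.6, or to 53% with error-free imaging.

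**5. Can 30 people tell 0.375 from 0.159?** With two covariates the Fisher-z standard error is 1 / √(30 − 2 − 3) = 0.20.
- z(0.375) = 0.394; 0.394 ± 0.392 gives r from 0.00 to 0.66.
- z(0.159) = 0.160; 0.160 ± 0.392 gives r from −0.23 to 0.50.
- Separation: (0.394 − 0.160) / 0.20 = 1.2 standard errors.

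The intervals overlap over most of their length.

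**6. Can the estimate size a later study?** For 80% power with two covariates, n = [(1.960 + 0.842) / z(r)]² + 5.
- r = 0.66: (2.802 / 0.793)² + 5, about 18.
- r = 0.16: (2.802 / 0.161)² + 5, about 306.
- r near 0.00: no finite size.

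An interval of 0.00 to 0.66 spans all of these.

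**7. How mixed is thyroid status at 6 months?** Section 6.0 says: "Most studies to show improvement in mood and/or cognition had a follow-up time of 6 months". Treat the cited 7 to 41 weeks as about ±2 SD of a log-normal. The median is √(7 × 41) = 16.9 weeks and the log-SD is ln(41/7)/4 = 0.442, implying a mean of 18.7 (19 is cited). About 73% are then not yet euthyroid at 13 weeks, but only 17% at 26 weeks (11 to 27% under other shapes tried). Most of the mixture has gone by the visit that an adjusted analysis would use. Section 2.0 also describes the sample as overt hypothyroidism, so starting severity varies within a narrower band than Section 4.1 alone suggests.

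**The case for a change.** The best case for adding the estimate is that it costs one paragraph and no new data, targets the one covariate that the protocol's theory singles out, and would be fixed in advance. Several thyroid tests and two follow-up intervals are available, so an adjustment chosen after seeing the results would be open to selection. Labelled as supportive and kept outside the false-discovery family, it would leave the planned tests untouched.

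Much of this stands. The limit on interpretation is real, and if a thyroid adjustment is ever reported, naming one variable and one interval beforehand is good practice. What does not stand is the claimed gain. The added coefficients would carry no significance claim. They would need two warnings: that a fall in r does not show absence of a link, and that a surviving r does not exclude shared cause. Under those terms no result changes what the trial concludes.

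The covariate is also debatable. TSH is the titration target, so successful treatment draws final values together and change in log TSH then mostly reflects the starting level. Free T4 is measured too and may serve as well. Adjusting for the intended driver of change is itself a matter of judgement.

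**Conclusion.** No change is needed. The age-only analysis answers the question posed for cognition, which is whether the changes correlate, and its error rate against that hypothesis is sound. It does not answer whether the correlation goes beyond shared thyroid recovery, and the protocol does not claim that it does.

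The size of any shared component is unknown from the documents. Under the assumed loadings it runs from trivial (0.3: significant in 7.5% of trials against a nominal 5%) to dominant (0.7: 79%), while Section 2.0 itself cites evidence both for and against the thyroid links. Even at the strong end, an adjusted estimate from 30 people separates link from no link by only about 1.2 standard errors, under the stated reliabilities of 0.6 and 0.8.

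The sponsor may report an age-and-thyroid partial correlation as low-priority description, over the same interval as the planned estimate and with a confidence interval. It should not be offered as a basis for sizing a later study. The point that matters for reporting is to describe a positive Aim 3 result as an association, which is how the protocol already frames it.

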1.0 Project Summary/Abstract

The ability to promote and support remyelination has wide-ranging implications for a number of neuropsychiatric conditions from multiple sclerosis to major depression. Pre-clinical evidence has demonstrated that thyroid hormone treatment, in the form of triiodothyronine (T3) or tetraiodothyronine (T4), can promote and support remyelination by increasing myelin basic protein mRNA and protein, oligodendrocyte proliferation and maturation, and fractional anisotropy (a diffusion imaging measure of white matter integrity). Pilot data from our own studies suggest that baseline thyroid status is correlated with the integrity of white matter tracts associated with major depression. *To date, the impact of thyroid hormone administration on white matter tracts has not been studied in vivo in adult humans.* The purpose of the proposed pilot study is to examine changes in white matter tract integrity using high angular diffusion imaging and multi-component relaxometry in a population of subjects clinically indicated to receive thyroid hormone for hypothyroidism. We will scan patients with hypothyroidism at the initiation of treatment and at three and six months after starting thyroid hormone treatment. We will also administer scales assessing mood and cognition which have been shown to correlate with white matter integrity. We hypothesize that thyroid hormone treatment will be associated with an increase in fractional anisotropy, a decrease in radial diffusivity, and an increase in the myelin water fraction (markers of improved myelination) that will correlate with improvements in cognition and mood ratings. If successful, this will be the first demonstration of improved white matter integrity with thyroid hormone replacement and pave the way for therapies designed to restore structural brain connectivity.

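### The Aim 3 analysis in Section 9 lists only cognitive scores, so the mood component of Hypothesis 3 has no written test

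*Combined protocol and SAP*

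**What the plan says.** **The promise.** Specific Aim 3 (Section 3.0) is "To correlate changes in white matter integrity with improvement in cognition and mood". Hypothesis 3, in the same section, names three outcomes expected to improve along with white matter integrity: psychomotor processing speed, executive function and mood, the last "with mood measured with lower depression severity ratings". The abstract (Section 1.0) says the same of the imaging changes, "that will correlate with improvements in cognition and mood ratings".

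**The data.** Section 6.0, under Behavioral Assessment, states: "Depression severity will be assessed with the PHQ-9 and the IDS". All assessments fall at baseline, 3 months and 6 months, and the PHQ-9 is also given every two weeks between sessions.

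**The analysis.** Section 9.0 has one sentence for Aim 3. It specifies bivariate correlations and partial correlations controlling for age, "between changes in FA, RD, and MWF and changes in executive function and processing speed performance scores". For multiplicity, Section 9.0 will report unadjusted and false discovery rate p-values, "basing the adjustment on the numbers of tests performed within each area". The areas are not defined.

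**The concern.** The outcome list in the Aim 3 sentence is closed: it has no wording that would make the two cognitive domains examples of a longer list. Mood, depression, the PHQ-9 and the IDS appear nowhere in Section 9.0. An analyst who follows that section literally will put no mood score into any Aim 3 correlation.

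What is at stake is a stated hypothesis, repeated in the abstract, for which participants complete mood forms throughout the study. Section 9.0 also says that data from this sample will feed power calculations for later studies, and the plan does not say which mood estimate, if any, would serve that purpose.

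**Working it through.** The plan gives no figure for this point, so there is none to reproduce. The check is a comparison of sections, followed by a count of what is missing and what adding it would cost.

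**Step 1: aim against analysis.**

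| Outcome in Hypothesis 3 (Section 3.0) | Measure (Section 6.0) | In the Aim 3 sentence (Section 9.0)? |
|---|---|---|
| Processing speed | NIH Toolbox | Yes |
| Executive function | NIH Toolbox | Yes |
| Mood (depression severity) | PHQ-9, IDS | No |

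Two of the three outcomes are carried through and one is not. The sentence is complete, with no sign of redacted or lost text.

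**Step 2: size of the gap.** Imaging measures: FA, RD and MWF = 3, each taken as one summary value (an assumption). Mood scales named under Behavioral Assessment: PHQ-9 and IDS = 2. Missing associations per change window: 3 x 2 = 6. If bivariate and age-partial versions count separately: 6 x 2 = 12.

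**Step 3: cost to the cognitive tests.** Assume the Benjamini-Hochberg method at 0.05 two-sided, n = 30 with complete data, each association counted once, and 3 imaging measures x 3 Toolbox tests = 9 cognitive associations in one window. The strictest step is 0.05/m. As a correlation it is |r| = t / sqrt(28 + t^2), where t is the two-sided critical value on 28 degrees of freedom.

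- Cognition alone, m = 9: 0.05/9 = 0.0056, t = 3.004, |r| = 3.004 / sqrt(28 + 9.03) = 0.494.
- Cognition and mood in one family, m = 9 + 6 = 15: 0.05/15 = 0.0033, t = 3.208, |r| = 3.208 / sqrt(28 + 10.29) = 0.518 (0.52 in round terms).
- Mood as its own area, m = 6: 0.05/6 = 0.0083, t = 2.839, |r| = 2.839 / sqrt(28 + 8.06) = 0.473. Cognition stays at 0.494.

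**Step 4: precision of the mood estimate.** For an illustrative observed r = 0.3 at n = 30, the 95% confidence interval is tanh(atanh(0.3) ± 1.96 / sqrt(27)) = tanh(0.310 ± 0.377) = -0.07 to 0.60. Adding the analysis gives an estimate for planning later work, but not a precise one.

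**The case against.** The strongest reply is that the omission is only apparent. The aim itself is to correlate imaging change with cognition and mood, and Section 9.0 says that Aim 3 will be analysed by correlation. Read together, they supply the method for mood, and any sensible analyst would run it. Much of this stands: the technique can be inferred, and the gap looks like a slip. What cannot be inferred is which mood scores enter and in which false discovery rate area they are counted. The reply also depends on the analyst departing from the only sentence that lists the variables.

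Three stronger readings are tempting, and the documents do not support them.

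- *Half of the hypothesis is abandoned.* Mood is one of three named outcomes, and nothing suggests that the investigators decided to drop it.
- *Late choice of mood scale and window inflates false positives.* Any such figure depends on assumed correlations among scales and windows. The planned false discovery rate adjustment limits the error if every test is counted. The missing window is not peculiar to mood either, since Section 9.0 gives none for cognition. Such figures do not measure the omission.
- *Three mood scores are available at follow-up.* Section 6.0 lists the clinician-rated and self-report IDS together once, at screening, separated by a slash. For behavioural assessment it names only the PHQ-9 and the IDS. Separate IDS versions at 3 and 6 months are an assumption.

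It is also fair to say that this is a single-group pilot of 30. Because Section 4.2 excludes major depressive disorder, the range of mood change may be narrow. That limits what the mood analysis can show, but does not remove the mismatch.

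**Conclusion.** The inconsistency is real and modest. Section 9.0 contains no mood test, although the abstract, Specific Aim 3 and Hypothesis 3 all promise one. Most likely this is a drafting omission, but under the text as it stands the mood component of Hypothesis 3 is untested on data the study already collects. Aims 1 and 2 and participant safety are not affected.

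This conclusion rests on the text alone. The counts and thresholds describe only the cost of repair. They depend on the assumed 9 cognitive associations, single summary imaging values, one change window and 30 complete participants. The plan should be corrected before the data are analysed.

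**What to change.** In Section 9.0, extend the outcome list in the Aim 3 sentence so that, besides the two cognitive domains, it includes change in depression severity (PHQ-9 total and IDS total), using the same bivariate and age-partial correlations. Say which IDS version supplies the total. State that mood is its own area for the false discovery rate adjustment.

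It would help to give the expected sign: lower mood scores are better, so the hypothesis implies negative correlations with change in FA and MWF and a positive one with change in RD.

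Naming one primary mood score and a baseline-to-6-month window is optional. Section 6.0 offers some support for 6 months: "Most studies to show improvement in mood and/or cognition had a follow-up time of 6 months".

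The cost is one line of text, no new data, and the 6 associations per window counted above (12 with the age-partial versions). With mood as its own area, the thresholds for the cognitive tests do not move.
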